#### ***End-of-treatment assessments***

The end-of-treatment assessments will include: Pharmacy fill/refill data, HAART medication adherence measures, HAART pill counts, TLFB for heavy drinking, OCDS, PEth, HIV drug resistance testing, HIV biological markers (CD4 lymphocyte count and HIV RNA levels), liver enzymes, platelet counts, hemoglobin, creatinine, sexual risk behavior assessment, SAFTEE, BAC, ASI, BSI, SIP, Brief Pain Inventory, TSR, SF-12, the Substance Use Survey, and patient satisfaction.

#### ***Follow-up assessments***

Follow-up assessments at 9 months and 12 months will include: Pharmacy fill/refill data for HAART, HAART medication adherence measures, HAART pill counts, TLFB for heavy drinking, OCDS, PEth, HIV drug resistance testing, HIV biological markers (CD4 lymphocyte count and HIV RNA levels), liver enzymes, platelet counts, hemoglobin, creatinine, sexual risk behavior assessment, BAC, ASI, BSI, SIP, Brief Pain Inventory, TSR, SF-12, and Substance Use Survey.

#### **Reasons for discontinuation/transfer**

APPROVED BY THE YALE UNIVERSITY IRB 10/11/2018 VALID THROUGH 10/13/2019  
If a patient develops significant psychiatric difficulties (suicidal or homicidal ideations, or psychosis) they will be referred to an independent psychiatrist for evaluation. The psychiatrist will determine whether patients can continue to safely receive care for their heavy drinking in the Nathan Smith Clinic or should be referred for alternate treatment.

**Table 1: Summary of Study Assessments**

	Wk -1	Wk 0	Wk 2	Wk4	Wk 6	Wk 8	Wk 12	Wk 16	Wk 20	Wk 24	Mn 9	Mn 12
History (demographic and clinical data) and physical exam	X											
Chart review for historical genotypic information	X											
SCID	X											
AUDIT	X											
OPRM1 genotyping	X											
Hepatitis B and C serologies	X											
Urine pregnancy test	X			X		X	X	X	X			
Liver enzymes (AST, ALT, GGT)	X			X		X	X	X	X	X	X	X
CBC, chemistries	X			X		X	X	X	X	X	X	X
CD4 count and HIV RNA	X			X		X	X	X	X	X	X	X
Standard HIV drug resistance testing and ultra-deep sequencing	X			X		X	X	X	X	X	X	X
Pharmacy fill/refill data for HAART adherence	X						X			X	X	X
Urine Drug Screen (for THC, opioids, coke, benzos at baseline; for opioids at other timepoints prior to VIVITROL injection)		X		X		X	X	X	X			
ACTG HAART medication adherence		X	X	X	X	X	X	X	X	X	X	X
HAART Persistence Questions		X	X	X	X	X	X	X	X	X	X	X
Visual Analog Scale (10cm): Adherence		X	X	X	X	X	X	X	X	X	X	X
Morisky 4-item Adherence Scale		X	X	X	X	X	X	X	X	X	X	X
Time-Line Follow Back (TLFB) for alcohol consumption	X		X	X	X	X	X	X	X	X	X	X
Alcohol Craving analog scale		X		X		X	X	X	X	X	X	X
OCDS		X		X		X	X	X	X	X	X	X
Substance Use Survey		X		X		X	X	X	X	X	X	X
PEth testing		X				X			X			X
Breathalyzer test (BAC)		X	X	X	X	X	X	X	X	X		
Sexual risk behaviors		X		X		X	X	X	X	X	X	X
SF-12		X		X		X	X	X	X	X	X	X
TSR				X		X	X	X	X	X	X	X
ASI-Lite		X								X		X
BSI		X								X		X
SIP		X								X		X
Brief Pain Inventory (+ Supplement)		X								X		X
SAFTEE		X	X	X	X	X	X	X	X	X		
VIVITROL injection		X		X		X	X	X	X			
Counseling Session		X	X	X	X	X	X	X	X			
Assessment compensation	X			X		X	X	X	X	X	X	X
Patient satisfaction survey						X			X			

4. **Statistical Considerations:** Describe the statistical analyses that support the study design.

***Data monitoring***

Our Web-based computer system, TrialDB, for data collection is used by the research assistant to administer the research instruments from any computer with Internet access. TrialDB is a Web-accessible, multi-disciplinary database for study- or disease-specific clinical research data designed to store the focused data required for clinical trials and clinical research studies. TrialDB is "open-source" software developed [REDACTED] at the Yale Center for Medical Informatics (YCFMI) and is being used at Yale and outside Yale to support clinical trials and clinical research. TrialDB has a large number of advanced features for data management and monitoring, including standard web reports and exports to SAS, SPSS, and SQL.

The core of this system will consist of a database hosted on a network of secure servers that are capable of collecting and storing data using Web-based applications that are accessed by remote users via standard Internet browsers such as Netscape or Microsoft's Internet Explorer. The system meets the highest security and reliability standards. All connections to the systems are secured and encrypted using 128-bit strong encryption protocols and only authorized users are able to access the system. The core of this system will consist of a SQL Server database and a Web server capable of collecting data and storing data using Web-based applications that are accessed by remote users via Microsoft's Internet Explorer. The system meets the highest security and reliability standards. All connections to the systems are secured and encrypted using 128-bit strong encryption protocols and only authorized users are able to access the system. All data is stored and backed up on servers located in a secured environment. Electronic files of all study data can be transferred securely to designated and authorized persons at any point during or after the study. At the request of the Principal Investigator, the host will erase all data from its systems and backed up data. This approach complies with security requirements and is consistent with other current projects that are being conducted.

***Statistical analyses***

General considerations: Statistical procedures and models for analyzing data have been selected according to the research hypotheses being investigated and the types of data available. In general, p-values <0.05 will be considered statistically significant. When necessary, however, we will use appropriate corrections of p-values to account for multiple statistical tests. Statistical analyses will be conducted on an intention-to-treat sample using SAS Release 8.1 (SAS Institute, Inc., Cary, NC) and SPSS 14.0 (SPSS Inc., Chicago IL) statistical packages. Where appropriate, hypotheses will be tested by independent statistical analyses using Mixed Models procedure to test for significant effect of group assignment (VIVITROL vs. placebo), time, and the interaction between group assignment and time. Loss to follow-up is of concern in longitudinal analyses, particularly if loss to follow-up is differential. We plan to use established strategies (> 90% follow-up) to reduce loss to follow-up [122, 124]. A benefit of the mixed effects models approach is that subjects who do not have complete information on the outcome variable can be included, provided that missing data is missing at random.

**Specific Aim 1:** To compare the efficacy of VIVITROL +MM/MC versus placebo +MM/MC on adherence to HAART.

**Hypothesis 1:** VIVITROL +MM/MC will lead to improved adherence to HAART when compared to placebo + MM/MC.

HAART medication adherence, specifically focusing on the proportion of patients achieving 95% or greater HAART adherence (See justification for this threshold in Section B.7.), will be evaluated using pharmacy fill/refill data on a monthly basis and self-report. For each month of the 24-week treatment period, and the 9 and 12 month follow-up periods, we will calculate the number of days of HAART medication adherence. Because HAART, the simultaneous use of  $\geq 3$  antiretroviral medications, is considered the standard of care for HIV-infected individuals, patients will be classified as adherent when their regimen medication possession ratio (MPR) (calculated as the days' supply of medication divided by the number of days between the first fill and the last refill [84]) is  $> 0.95$ , signifying greater than 95% adherence. We will also capture the MPR of all anti-retroviral medications. In prior work, we have shown that over a one year study period in VACS, the HAART MPR was 70% compared to 77% of any anti-retroviral total (Kim et al, unpublished). For patients who are on HAART but less than 95% adherent, we will determine what proportion of this group achieved greater than 95% adherence.

For primary outcome analysis, both aggregate and stratified analyses will be carried out to compare the proportion of participants in each of the two groups who achieve  $\geq 95\%$  adherence during the last four months of observation.

The probability of achieving the primary outcome will be modeled using logistic regression analysis. An unadjusted model (treatment) and models that include covariate adjustment (treatment plus other predictor variables eg depression, race, opiate receptor genetics, CD4 level, viral load level) will be executed.

In addition and, as appropriate, linear mixed effects models will be used to assess changes in adherence over the six months of observation. Models will include a fixed effect for treatment status, time as a continuous variable representing the month of observation, and the interaction between treatment and time in order to assess difference in slopes of change by treatment status. Random effects will be included to account for intra-subject correlation of repeated measures. Additional factors that may impact rate of change in adherence include time-varying covariates such as CD4 and viral load. Model fit will be assessed with analysis of residuals and other standard methods for assessing goodness-of-fit [136].

There are multiple strategies to measure adherence (See Sections B.8. and B.9.). Based on strong evidence in support of this strategy [72, 88, 89], we have chosen to examine the percentage of patients, using pharmacy fill-refill data, who achieve 95% or better adherence to their HAART treatment as our primary outcome measure of adherence [60, 117]. We will also examine adherence using self-report data collected using AIDS Clinical Trials Group (ACTG) assessment. Patients will be classified as meeting the criteria for greater than 95% adherence if they are adherent 29-30 days out of the past 30 days. We will use the Chi-Square test to compare the proportion of patients in each randomization group meeting these criteria during each month of the study. The t-test will be used to compare HAART medication adherence between the two treatment conditions based on self-report.

**Specific Aim 2:** To compare the efficacy of VIVITROL +MM/MC versus placebo +MM/MC in reducing days of heavy drinking.

**Hypothesis 2:** VIVITROL +MM/MC counseling will lead to greater reductions in the number of days of heavy drinking when compared to placebo + MM/MC.

We plan to use a standard alcohol consumption outcome, the number of days of heavy drinking (4 or more drinks per drinking occasion for women and 5 or more drinks per drinking occasion for men) in the past 30 days. This measurement was one of the outcomes

APPROVED BY THE YALE UNIVERSITY IRB 10/11/2018 VALID THROUGH 10/13/2019  
that differed between the control and VIVITROL group in the recent study of extended release VIVITROL [57]. The planned analyses for this outcome will include examining the number of days of heavy drinking over the 24-week treatment period and at the 9-month and 12-month follow-up periods. This measure will be based on self-reported alcohol use from the Time-Line Follow Back. Since individuals may choose to leave during treatment and a small proportion could be lost to follow-up we plan to use repeated measures analysis of variance with the MIXED Models procedure. The MIXED Models procedure was designed for unbalanced repeated measures with missing data, allowing for intra-participant serial correlation and unequal variance and covariance structure across time [137]. A repeated measures analysis of variance in the Mixed Models procedure takes into consideration differences that may emerge over time, and we will use this procedure to test for a significant treatment effect, time effects, and the interaction of these two on the primary outcome measure.

**Specific Aim 3 (Exploratory):** To explore the effect of VIVITROL +MM/MC versus placebo +MM/MC on biologic outcomes including:  
3a) HIV markers—viral mutations (using standard assays and ultra-deep sequencing), CD4 lymphocyte count and HIV RNA level; and  
3b) Liver function tests

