Measuring HAART adherence can be challenging and can include self-report, pill count, and electronic monitoring. One additional assessment of adherence that is amenable to measurement, and will be used in the current trial, is “persistence”. Persistence is defined as the continuous refill of prescribed medications using pharmacy data. Persistence can be conceptualized as necessary, though not sufficient, for adherence to occur. Without the filling and refilling of medications, patients can not adhere to their medications. Unlike other adherence measurements such as self-report, pill count, or electronic monitoring, persistence is an objective measure that does not rely on provider or patient action to obtain. It can also be updated easily so as to avoid the pitfall of defining an individual as adherent at a single point in time and miss their later non-adherence [75]. Persistence has been used to measure patients’ adherence to HAART [80], to NTX for alcohol treatment [81] and to investigate refill behaviors with drug regimens such as statins and anti-hypertensive medications used for other chronic diseases [82, 83]. There are a number of ways that pharmacy refill data can be analyzed to create persistence measures of adherence. The medication possession ratio (MPR) is a commonly used metric that has been validated with virologic response [84-86]. It is calculated as the days’ supply of medication divided by the number of days between the first fill and the last refill and represents the maximum possible adherence that a patient can attain over a defined refill period. The MPR has the capacity to detect inconsistent adherence patterns, is low-cost and has been validated [87]. Within HIV, pharmacy refill of HAART has been used to characterize the following associations: CD4 levels and HAART initiation [88], intermittent use of HAART and mortality [72], as well as HAART adherence and virologic response [89].

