***Baseline and in-treatment assessments***

Prior to entrance into the study each patient will undergo a medical history, physical and laboratory assessments (Complete blood count (CBC), chemistry panel, and viral hepatitis serologies). A urine pregnancy test will be performed at baseline and each month thereafter and must be negative throughout the study. The research assistant will collect demographic data including items such as marital status, highest level of education completed, employment, substance use history, duration of HIV disease, and a detailed HAART medication history. Charts will be extracted to collect information including medical co-morbidities, prior CD4 lymphocyte cell counts and HIV RNA levels, HAART medication history, historical genotypic information from prior HIV drug resistance testing, and patient satisfaction data.

**HAART medication adherence**, with the goal of determining the proportion of patients achieving 95% or greater HAART adherence, will be measured using pharmacy fill/refill data using the medication possession ratio defined as the total days supply/refill interval. Information needed to calculate the medication possession ratio is readily available in the patient's pharmacy data. With subject written consent, we will call the pharmacy designated by the subject to determine refill dates and days supply of medication. In addition, self-reported HAART adherence will be collected using the AIDS Clinical Trials Group (ACTG) assessment [128]. Patients will be asked how often they took each of their medications during the preceding month. We will also be conducting the Morisky 4-item adherence scale, a brief "persistence" measurement for medication persistence, and a single item visual analog scale for adherence. We will use a valid adjustment strategy [129] to resolve discrepancies between the various methods of assessing HAART adherence. The use of electronic drug monitoring in the form of medication event monitoring system (MEMS) caps for measuring HAART adherence was considered as it offers the best correlation with virologic outcomes [130]. However, several documented disadvantages such as expense, lack of feasibility for most

APPROVED BY THE YALE UNIVERSITY IRB 10/11/2018 VALID THROUGH 10/13/2019  

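### The primary endpoint's medication possession ratio stops counting at the last refill, so a patient who refills on time and then stops HAART can be scored adherent, and a patient with one fill cannot be scored

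*Combined protocol and SAP*

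**What the plan says.** Three places define the ratio.

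- **Section V.2 Background, on pharmacy refill:** supply is "divided by the number of days between the first fill and the last refill and represents the maximum possible adherence" over a refill period. The same paragraph recommends refill data because they avoid "the pitfall of defining an individual as adherent at a single point in time and miss their later non-adherence".
- **Section V.3, Baseline and in-treatment assessments:** "medication possession ratio defined as the total days supply/refill interval". The interval is not defined and has no stated end date.
- **Section V.4, Statistical analyses, Specific Aim 1:** the days' "supply of medication divided by the number of days between the first fill and the last refill". A patient is adherent when the regimen ratio is above 0.95, "signifying greater than 95% adherence".

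The pharmacy measure is the primary one: the plan examines the percentage of patients, "using pharmacy fill-refill data, who achieve 95% or better adherence to their HAART treatment as our primary outcome measure of adherence". The primary comparison is of the proportions reaching the threshold of "adherence during the last four months of observation".

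The plan has no rule for time after the last refill, for patients with no fill or one fill, for whether the last fill's supply enters the numerator, or for capping the ratio at 1.

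**The concern.** The endpoint is meant to describe a fixed period, but the denominator ends at an event that the patient controls. This has three consequences.

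1. **Stopping is invisible.** After the last refill no further days enter the denominator. A patient who refilled on time and then gave up HAART keeps a ratio of at least 1.
2. **Late refilling can be hidden.** If the last fill's supply is counted, one extra fill's worth of days is credited with no matching time in the denominator. The assessments section, which speaks of total supply, suggests this reading, but the plan does not settle it.
3. **Some patients have no score.** With one fill, first and last fill coincide and the denominator is zero.

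This ratio decides every patient's primary outcome. The population is heavy drinkers chosen for poor adherence, and the trial is planned at only 72% power. The formula also misses the later non-adherence that the Background gives as a reason for using refill data.

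**Working it through.** **Assumptions not in the documents.** Fills are for 30 days. The last four months are taken as 112 days (16 weeks) ending at week 24; Specific Aim 1 elsewhere speaks of six months of observation. Day 0 is the first day of the window, with no stock carried in.

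**Formulas.** MPR as written = supply ÷ (last refill day − first fill day). Fixed-window coverage = days with supply on hand ÷ 112.

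| Fill days | MPR, last fill counted | MPR, last fill excluded | Days covered of 112 |
|---|---|---|---|
| 0, 30, then none | 60/30 = 2.0 | 30/30 = 1.0 | 60 (54%) |
| 0, 30, 60, then none | 90/60 = 1.5 | 60/60 = 1.0 | 90 (80%) |
| 0, 47, 94 | 90/94 = 0.957 | 60/94 = 0.638 | 30 + 30 + 18 = 78 (70%) |
| 0 only | 30/0, undefined | 0/0, undefined | 30 (27%) |
| 0 only, 90-day fill | 90/0, undefined | 0/0, undefined | 90 (80%) |

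The first two patients pass on either reading. For the third, the unsettled last-fill rule alone changes the primary outcome. With a 122-day window, the first patient's coverage is 60/122 = 49%.

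Not every patient who stops will pass. With the last fill excluded, the mean gap between fills before stopping must be below 30/0.95 = 31.6 days.

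**The plan's power.** From Sample size estimation: 154 patients (77 per arm at 1:1), 20% against 40%, alpha 0.05 (two-sided assumed). Let d be the difference in rates and n the number per arm. The pooled two-proportion formula with a continuity correction of 1/n is

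power = Φ[(d − 1/n − 1.96·SE₀)/SE₁]

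where SE₀ uses the pooled rate and SE₁ the separate rates.

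- SE₀ = √(2 × 0.30 × 0.70/77) = 0.0738
- SE₁ = √((0.20 × 0.80 + 0.40 × 0.60)/77) = 0.0721
- (0.20 − 0.0130 − 0.1447)/0.0721 = 0.586, so power is 72.1%

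This matches the stated 72%. Without the correction it is 77.8%.

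**Illustration of misclassification.** Suppose a share s of truly non-adherent patients is scored adherent. The observed rate is then p + (1 − p)s.

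| s active | s placebo | Active rate | Placebo rate | Power |
|---|---|---|---|---|
| 0 | 0 | 40% | 20% | 72.1% |
| 10% | 10% | 46% | 28% | 57.5% |
| 20% | 20% | 52% | 36% | 45.1% |
| 10% | 20% | 46% | 36% | 19.3% |
| 20% | 10% | 52% | 28% | 82.7% |

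Equal shares shrink a real difference. Unequal shares can shrink it or enlarge it. The values of s are chosen for illustration; the documents offer no basis for estimating them.

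**The case against.** **The same paragraph plans a monthly evaluation and a monthly count of adherent days.** A calendar month without supply might then show up as zero days. This is a real feature of the plan, and it shows that two pharmacy measures stand side by side unreconciled. But the stated rule for calling a patient adherent is the MPR. Applying that MPR month by month would make matters worse, because with 30-day fills a month will commonly hold a single fill.

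**The MPR is described as commonly used and validated, over a defined refill period.** In the Background's own formula, that period runs from first fill to last refill. Validation for other purposes does not make it measure adherence in a fixed four-month window.

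**Self-report and the planned adjustment for discrepancies between methods might catch patients who stop.** Neither is written into the primary classification.

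**The sub-points depend on the reading.** This is partly right. The late-refill example needs the last fill counted. Single fills would be rarer if the ratio ran over all 24 weeks. The on-time refiller who then stops within the measured period passes on either last-fill reading, and a single fill is unscorable on both.

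**The power figures are not evidence.** They are only an illustration. If the planning rates of 20% and 40% are themselves MPR-scored, they already contain part of this error and the drop in power would be overstated. Taken fully, the 20% scenario would then imply a true placebo rate of (0.20 − 0.20)/0.80 = 0%. It is also right that, if naltrexone does not affect refill behaviour at all, misclassification is equal in expectation and type I error is not inflated.

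**Scoring uncovered days as non-adherent is itself a choice.** It affects dropouts, provider-directed interruptions and fills at a pharmacy other than the designated one. This stands, and the fix must address it.

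**Conclusion.** The concern holds. The rule as written can give a wrong primary outcome, so this is more than missing detail: on-time refilling followed by stopping HAART is scored as success on either treatment of the last fill, and a patient with one fill has no score. This follows from the formula itself; the 30-day fills and 112-day window serve only the worked examples.

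The number of patients affected and the direction of the bias are unknown, because the documents give neither a HAART lapse rate nor a fill length. The power range of 58% to 45% for equal misclassification of 10% to 20%, and 19% to 83% for unequal misclassification, rests on assumed shares and on planning rates that are free of this error. The stated sample size calculation is not in error. Because the rule determines the primary outcome for every patient, it must be fixed before unblinding.

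**What to change.** Define the primary measure as the number of days with the full HAART regimen on hand divided by all days in the fixed last-four-month window, capped at 1 and not cut off at the last refill. Give the window's start and end by study week. Uncovered days after the last refill then count as non-adherent, and patients with no fill or one fill are scored on the same denominator as everyone else.

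State before unblinding:

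- how stock carried into the window and overlapping fills are handled;
- which days, if any, are excluded, with explicit rules for dropouts, provider-directed interruptions and fills outside the designated pharmacy;
- that this measure replaces the differing MPR wordings in the Background, the assessments section and Specific Aim 1, and how the monthly count relates to it.

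The cost is SAP wording, the decisions just listed and some programming. No new data are needed: the plan already says that "we will call the pharmacy designated by the subject to determine refill dates and days supply of medication", and Table 1 schedules pharmacy data at weeks −1, 12 and 24, so stock held at the start of the window can be derived. Adherence rates will look somewhat lower than under the present formula.

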Randomization: Eligible participants will be randomly assigned to VIVITROL + MM/MC or placebo + MM/MC by the investigational pharmacist. All staff, other than this individual and the study biostatistician(s), will be blind to treatment allocation. Subjects will be assigned to one of the two conditions using stratified randomization. There will be 6 strata: (a) participating clinic (3) and (b) alcohol abuse/dependence (Yes/No; 2) in the randomization scheme.

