clinical settings, and the likelihood of underestimation of adherence due to patients' "pocket dosing" their medication or removing more than one dose for each bottle opening, lead us to choose the other three methods in order to measure adherence [130].

We anticipate that a number of HIV-infected patients with heavy drinking may not be prescribed HAART medications due to their providers' concerns about poor medication adherence. While such patients do not meet the second eligibility criterion, we will encourage interested patients to discuss the possibility of resuming HAART with their HIV providers, such that they could be considered for enrollment at a later date. In addition, in an effort to include this target sub-population without mandating the usual 90 days of HAART-adherence data, we will determine their baseline adherence after 30 days; patients will be invited to present for an eligibility assessment one month after their first HAART prescription. We will use a simple 30-day pill count to calculate their baseline adherence.

**The Morisky scale** is a commonly used, validated, 4-item self-reported adherence measure that has been shown to be predictive of medication adherence. It includes two items that measure intentional medication non-adherence.

**Alcohol Use** will be assessed using the Time-Line Follow Back Interview (TLFB) [131] which will obtain the quantity/frequency of alcohol consumed for each day in the past month (baseline) and since the prior visit. TLFB has good test-retest reliability and good validity [131]. In addition, in order to better determine the "category" of drinking behavior of a subject at baseline, we will use the Alcohol Use Disorders Identification Test (AUDIT) [26], a valid instrument for categorizing alcohol consumption.

**The Obsessive-Compulsive Drinking Scale (OCDS)** is a 14-item, self-administered questionnaire for characterizing and quantifying the obsessive and compulsive cognitive aspects of craving and heavy (alcoholic) drinking, such as drinking-related thought, urges to drink, and the ability to resist those thoughts and urges.

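### Baseline adherence and baseline heavy drinking are collected but given no role in the Aim 1 and Aim 2 models, and the primary stratified analysis does not name its strata

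*Combined protocol and SAP*

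**What the plan says.** **What is collected.** Table 1 marks "Pharmacy fill/refill data for HAART adherence" at week -1. The Time-Line Follow Back is also marked at week -1, and the section on baseline and in-treatment assessments describes it as an interview "which will obtain the quantity/frequency of alcohol consumed for each day in the past month (baseline) and since the prior visit". Patients who have only just started or resumed HAART get a different baseline measure: "We will use a simple 30-day pill count to calculate their baseline adherence".

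**How patients are randomised.** The Randomization paragraph states: "There will be 6 strata: (a) participating clinic (3) and (b) alcohol abuse/dependence (Yes/No; 2) in the randomization scheme".

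**Aim 1 analysis.** Under Statistical analyses, Specific Aim 1, "both aggregate and stratified analyses will be carried out to compare the proportion of participants in each of the two groups", without saying what the strata are. The outcome is then modelled by logistic regression, first with treatment alone and then with "models that include covariate adjustment (treatment plus other predictor variables eg depression, race, opiate receptor genetics, CD4 level, viral load level". In addition, where suitable, "linear mixed effects models will be used to assess changes in adherence over the six months of observation", including "the interaction between treatment and time in order to assess difference in slopes of change by treatment status". No sentence says whether the aggregate, stratified, unadjusted or adjusted analysis decides Hypothesis 1.

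**Aim 2 analysis.** A repeated-measures mixed model of heavy-drinking days tests treatment, time and their interaction. Baseline drinking is not mentioned.

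**Aim 3a analysis.** Here the plan does control for baseline differences, for CD4 count, HIV RNA, liver tests and FIB-4.

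**The concern.** The baseline value of an outcome is often its best single predictor. The plan uses baseline values for exploratory outcomes but names none for its two main aims, and the Aim 1 covariate list also omits both stratification factors. The Aim 1 mixed model does not fill the gap. It is supplementary, it tests a difference in slopes, and it does not say whether baseline counts as month 0.

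Leaving these terms out does not bias the randomised comparison. Two things are at stake:

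- **Aim 1:** power in a trial planned at only 72%, and freedom to choose among several candidate primary analyses after the data are seen.
- **Aim 2:** Hypothesis 2 is about a larger fall in heavy-drinking days, but the text fits several different tests with very different power. Baseline could be a covariate, the first time point, part of a change score, or unused.

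If dropout depends on baseline drinking or adherence, omitting baseline also weakens the missing-at-random assumption that the mixed models rely on.

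**Working it through.** **The plan's own power figure.** Inputs from Sample size estimation: 154 patients (77 per arm), 20% versus 40%, alpha 0.05, taken as two-sided. Pooled proportion 0.30.

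- Without continuity correction: Φ[(0.20 − 1.96·√(2·0.3·0.7/77)) / √((0.2·0.8 + 0.4·0.6)/77)] = 77.8%.
- With continuity correction, replacing 0.20 by 0.20 − 1/77: 72.1%, which reproduces the stated 72%.

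**Aim 1 simulation.** 20,000 null replicates (30% in both arms) and 20,000 alternative replicates per setting. Assumed: clinics of 50/52/52, 70% with an alcohol diagnosis, permuted blocks of 4 in the six strata, stratum SD 0.3 on the log-odds scale. Wald tests were each judged at their own simulated 5% critical value. The log odds ratio per SD of baseline adherence is not in the documents, so it is varied. The last two columns assume 10% of baselines missing at random and 20% new starters, whose pill count correlates 0.7 with the refill measure. The rule is the overall baseline mean plus a missingness indicator, plus an indicator for pill-count baselines.

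| log-OR per SD | Unadjusted | Strata only | Strata + baseline | With missing-baseline rule | Patients without baseline dropped |
|---|---|---|---|---|---|
| 0 | 78.8 | 78.8 | 78.8 | 78.1 | 74.5 |
| 0.4 | 78.2 | 78.2 | 79.1 | 78.4 | 74.9 |
| 0.7 | 78.9 | 78.4 | 81.6 | 80.2 | 76.3 |
| 1.0 | 79.1 | 78.9 | 84.8 | 82.9 | 79.3 |
| 1.3 | 78.7 | 78.6 | 87.1 | 84.9 | 81.6 |

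- With complete baselines the gains over the unadjusted test are 0, 0.9, 2.7, 5.7 and 8.4 points. A second run with new seeds gave 1.1, 2.6–3.4, 5.7 and 8.2–8.8 at log-OR 0.4, 0.7, 1.0 and 1.3. Monte Carlo error of a gain is about 0.4 points.
- With the missing-baseline rule the change runs from −0.7 to +6.2 points. Dropping patients gives −4.3 to +2.9.
- Against a model already adjusted for viral load (assumed correlation 0.3–0.7 with baseline adherence), strata plus baseline add about 1 to 8 points: for example 80.3 to 81.6 at log-OR 0.7 and correlation 0.7, and 79.2 to 87.1 at log-OR 1.3 and correlation 0.3.
- Type I error at the usual 1.96 cut-off: unadjusted 4.5–4.8%, strata plus baseline 5.0–5.4%, with the rule 5.2–5.4%.

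**Aim 2 calculation.** The plan gives no power for Aim 2. Assumed: 77 per arm, six 4-week periods, unit variance, correlation r of 0.4–0.6, normal approximation, and an effect with 80% power on the post-baseline mean (noncentrality 1.96 + 0.84 = 2.80). Let V be the variance of the post-baseline mean and c its covariance with baseline.

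- Covariate: variance ratio 1 − c²/V; power = Φ(2.80/√ratio − 1.96). Compound symmetry, r = 0.4: V = (1 + 5·0.4)/6 = 0.50, c = 0.40, ratio = 1 − 0.16/0.50 = 0.68, power 92%. At r = 0.5 and 0.6 the ratios are 0.57 and 0.46. Under AR(1) they are 0.96, 0.93 and 0.88.
- Mean change from baseline: ratio (V + 1 − 2c)/V. Compound symmetry, r = 0.4: (0.50 + 1 − 0.80)/0.50 = 1.4, power 66%.
- Baseline as a seventh time point, main effect: the effect shrinks to 6/7 and the variance becomes that of a seven-point mean.
- Treatment-by-time interaction with baseline included: noncentral chi-square, 6 df.

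| Reading of the Aim 2 test | Compound symmetry | AR(1) |
|---|---|---|
| Baseline as covariate | 92–98% | 81.5–84.8% |
| Mean change from baseline | 66–92% | 33–49% |
| Seventh time point, main effect | 68% | 71.5–72.6% |
| Interaction, constant effect | 38–70% | 19–35% |
| Interaction, linear build-up | 84–99% | 28–39% |
| Interaction, step after 12 weeks | 100% | 81–97% |

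The first three rows depend only on the average effect. A slope-difference test such as the one in the Aim 1 mixed model has 5% power for a constant effect over months 1–6. If baseline is month 0, it has 30.5–53.6% under compound symmetry and 15.6–23.2% under AR(1).

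**The case against.** **The covariate list is open.** It is given as examples, so baseline adherence could still be added, and the six randomisation strata are the natural reading of the stratified analyses. That is true, but an open list is not pre-specification and does not say which analysis decides.

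**The Aim 1 gain may be small.** This stands. Inclusion requires reported adherence below 95%, which narrows the range of baseline adherence. With the missing-baseline rule, the gain is material only at a log-OR of about 1.0 or more.

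**The adjusted model is not free.** It has up to seven terms besides the intercept for about 46 expected responders (30% of 154), and its Wald test runs slightly above 5%. This also stands, and the size is shown above.

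**Finding no power from strata depends on equalising test size.** Fair. At the ordinary 1.96 cut-off the unadjusted test is conservative under stratified randomisation (4.2%, 3.8% and 3.3% at assumed stratum SDs of 0.3, 0.7 and 1.0). Adding clinic and diagnosis then gains about 1, 3 and 5 points. This supports including the strata.

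**The Aim 2 spread mixes different tests, and serial correlation shrinks the covariate gain.** Correct: under AR(1) covariate adjustment moves 80% only to 81.5–84.8%. But the plan's text allows all of these tests. Reading baseline as the first time point is plausible, but it is not stated, and it gives 68–73% for the main effect.

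**Conclusion.** The concern holds, as a loss of efficiency and a gap in specification; it does not make the planned Aim 1 test invalid. Baseline refill adherence and baseline heavy-drinking days are collected and not named in the Aim 1 or Aim 2 models, and the stratified primary analysis does not identify its strata.

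For Aim 1 the benefit ranges from nothing to about 9 points of power with complete baselines, and from −0.7 to +6.2 under the assumed missingness. It rests on an assumed prognostic strength.

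Aim 2 is the stronger half. For the same constant effect at r = 0.4 under AR(1), power is 81.5% with baseline as covariate, 73% for the main effect with baseline as a time point, 33% for mean change and 19% for the interaction. These figures rest on assumed correlations and a normal approximation to a bounded count. The change is worth making because it is cheap; confidence in the size of the gain is moderate.

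**What to change.** **Aim 1.**

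- Make the primary test a logistic regression on treatment, clinic, alcohol abuse/dependence and continuous baseline adherence, with an indicator for new starters measured by pill count.
- Where the baseline possession ratio is missing or cannot be calculated, use the overall baseline mean plus a missingness indicator, so that every randomised patient stays in. Do not drop these patients.
- Report a standardised risk difference beside the odds ratio.
- State that the stratified analyses use the six randomisation strata. Keep these, the unadjusted model, the other logistic models and the linear mixed model as sensitivity or supporting analyses.

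**Aim 2.**

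- Fit the mixed model to post-baseline heavy-drinking days, with baseline heavy-drinking days, clinic and alcohol diagnosis as covariates.
- Make the average treatment difference over 24 weeks the primary contrast. Keep treatment-by-time as a named secondary test, since an effect that appears only late would favour it under most correlations tried.

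**Cost.** Analysis-plan wording and one missing-baseline rule; no new data. If baseline adherence is not prognostic, the extra terms cost up to about 0.7 points of power. The adjusted odds ratio is conditional (median standard error 0.369 unadjusted, 0.401 adjusted at log-OR 0.7), and test size rises from 4.5–4.8% to 5.2–5.4% with the rule. Baseline adherence will still combine two instruments.
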